05 SEP 2017

For internal use only

-----Checksum-----!Ver.!Created On - -
14e7f0d060e9c2824a7cda1b9b88bb3971203f7a 3.0 8/18/2017 8:41:12 AM - -

Protocol Amendment 2 Rationale

Amendment number:	Amendment 2
Rationale/background for changes:	

• The date of birth requirement has been eliminated from the study as it is not necessary for the design or the objectives of the study and will ease the recruitment constraint observed in the study.• The post last dose interval will be updated due to low number of eligible subjects identified within the existing intervals which puts at risk achieving adequate sample size.
– For the Year 8 survey: The new post last dose time interval may include children with ≥ 7 years and < 10 years between last dose.– For the Year 10 survey: The new post last dose time interval may include children with ≥ 10 years and < 13 years between last dose.– This post last dose time criteria has been added to inclusion criteria section for clarification.	

Protocol Amendment 2 Investigator Agreement

I agree:

- To conduct the study in compliance with this protocol, any mutually agreed future protocol amendments or protocol administrative changes, with the terms of the study agreement and with any other study conduct procedures and/or study conduct documents provided by GlaxoSmithKline (GSK) Biologicals.
- To assume responsibility for the proper conduct of the study at this site.
- That I am aware of, and will comply with, 'Good Clinical Practice' (GCP) or other applicable guidelines such as International Society for Pharmacoepidemiology (ISPE) guidelines for Good Pharmacoepidemiology Practices (GPP) and all applicable regulatory requirements.
- To ensure that all persons assisting me with the study are adequately informed about study-related duties and functions as described in the protocol.
- To acquire the reference ranges for laboratory tests performed locally and, if required by local regulations, obtain the laboratory's current certification or Quality Assurance procedure manual.
- To ensure that no samples (including serum samples) are retained onsite or elsewhere without the approval of GSK Biologicals and the express written informed consent of the subject and/or the subject's legally acceptable representative.
- To perform no other biological assays on the samples except those described in the protocol or its amendment(s).

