Universal hepatitis A vaccination was introduced in Panama in April 2007. Two doses of the vaccine were given to children at 12 and 18 months of age. The Expanded Program of Immunisation (EPI) of Panama had reportedly provided 53,417 and 7,104 doses of *Havrix* in Panama (first and second dose) during 2007 for an estimated coverage of 81% of the population receiving at least one dose of *Havrix* and 11% receiving both doses (complete series). In 2008, vaccination coverage rose as 99% of the eligible population received at least one dose of *Havrix* and 65% received the complete vaccination series (two doses) [GlaxoSmithKline Biologicals Clinical Study Report 112263].

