* Pass 2005, one-sided equivalence test of proportions (non-inferiority), alpha = 2.5%, power under equal proportions.

H0: group difference in expected % of subjects with anti-HAV concentrations $< \delta$ (P1-dose – P2-dose $< -10\%$)

Ha: group difference in expected % of subjects with anti-HAV concentrations $\geq \delta$ (P1-dose – P2-dose $\geq -10\%$)

**References used for the sample size calculation: [Racznik, 2013 and Hammitt, 2008]

8.3. Cohorts for Analyses at Years 8 and 10

The following cohorts will be defined separately for each epoch.

8.3.1. Total cohort at Year 8 or Year 10

The total cohort at Year 8 or at Year 10 will include all subjects enrolled in the study at Year 8 or Year 10 serosurveys, respectively. For the analysis of persistence, this will include subjects for whom data concerning persistence endpoint measures are available.

8.3.2. Total effective cohort at Year 8 or Year 10

The total effective cohort at Year 8 or Year 10 will include all enrolled subjects who have a valid ICF at Year 8 or Year 10 serosurveys, respectively.

8.3.3. According-to-Protocol (ATP) cohort for persistence at Years 8 or 10 (Amended: 24 July 2017)

The ATP cohort for persistence at Year 8 or at Year 10 will include all enrolled subjects:

- who have a valid ICF
- who have available assay results at Year 8 or Year 10 serosurveys, respectively.
- who have not received a hepatitis A vaccine other than Havrix.
- who do not have a history hepatitis A infection prior to study.
- who have available HAV vaccination records.
- who received either 1 or two doses of Havrix at selected health centres of Panama.
- who have ≥ 7 years and < 10 years between last dose and Persistence Visit 1 (Year 8) and children ≥ 10 years and < 13 years between last dose and Persistence Visit 1' (Year 10).

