## 2. STUDY DESIGN

This is an epidemiological, serial, cross-sectional, interventional, multi-centre study in Panama.

The following epochs will be analysed:

Group order in tables	Group label in tables	Group definition for footnote
1	Epoch 1 (Year 8)	Subjects with $\geq 7$ years and $< 10$ years between last Havrix dose and Persistence visit
2	Epoch 2 (Year 10)	Subjects with $\geq 10$ years and $< 13$ years between last Havrix dose and Persistence visit

The following dose group names will be used for the statistical analyses:

Group order in tables	Group label in tables	Group definition for footnote
1	1 Dose	Subjects received one dose of Havrix
2	2 Doses	Subjects received two doses of Havrix

Time interval between the last *Havrix* vaccination dose and the Persistence visit:

Sub-group order in tables	Sub-group label in tables	Sub-group definition for footnote
1	$\geq 7$ years and $< 8$ years	$\geq 7$ years and $< 8$ years between last Havrix vaccination and Persistence visit
2	$\geq 8$ years and $< 9$ years	$\geq 8$ years and $< 9$ years between last Havrix vaccination and Persistence visit
3	$\geq 9$ years and $< 10$ years	$\geq 9$ years and $< 10$ years between last Havrix vaccination and Persistence visit
4	$\geq 10$ years and $< 11$ years	$\geq 10$ years and $< 11$ years between last Havrix vaccination and Persistence visit
5	$\geq 11$ years and $< 12$ years	$\geq 11$ years and $< 12$ years between last Havrix vaccination and Persistence visit
6	$\geq 12$ years and $< 13$ years	$\geq 12$ years and $< 13$ years between last Havrix vaccination and Persistence visit

Age class at the first dose of Havrix:

Sub-group order in tables	Sub-group label in tables	Sub-group definition for footnote
1	[0 – 6 months[	Subjects aged less than 6 months at the time of the first dose of Havrix
2	[6 – 12 months[	Subjects aged between 6 months and 12 months at the time of the first dose of Havrix
3	[12 – 18 months[	Subjects aged between 12 months and 18 months at the time of the first dose of Havrix
...	...	...

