#### 3.2. Secondary objectives

- To assess geometric mean concentration (GMC) of anti-HAV antibodies, *approximately* 8 years and 10 years post vaccination with the last received dose of the complete series of *Havrix* (2 doses) and the partial series completion (1 dose) in Panama.
- To explore the non-inferiority of the 1-dose schedule of *Havrix* when compared to the 2-dose schedule in terms of the percentage of subjects with anti-HAV antibody concentrations  $\geq 15$  mIU/mL, *approximately* 8 years and 10 years after the last received vaccination dose.

*Criteria for evaluation: The lower limit of the 2-sided 95% CI for the difference (1-dose group minus the 2-dose group) of percentage of subjects with anti-HAV antibody concentrations  $\geq 15$  mIU/mL is greater than or equal to the pre-defined clinical non-inferiority limit of -10%.*

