#### *Demography*

The number of subjects enrolled as well as the number excluded from the ATP analysis will be presented.

The distribution of subjects by centre will be tabulated according to *Havrix* dose group.

Demographic characteristics such as age at the Persistence visit, age/age class [months] at the time of first and second dose of *Havrix* administration, time interval [months] between *Havrix* dose 1 and dose 2 administration, time since last *Havrix* dose [years], sex, geographic ancestry, rural and urban residency of the subjects will be summarized using descriptive statistics per dose group and overall:

- Frequency tables will be generated for categorical variables such as sex.
- Mean, median, standard deviation, minimum and maximum will be provided for continuous data such as age.

The analysis will be performed on the Total enrolled and ATP cohorts for the demographic part.

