***Within group analysis***

For the subjects who had received either one dose or two doses of *Havrix*, at each serosurvey (**approximately** 8 years and 10 years after the last vaccine dose):

- Percentage of subjects with concentrations above the cut-off ( $\geq 15\text{mIU/mL}$ ) with exact 95% CI will be calculated [seropositivity rate].
- Geometric mean concentration (GMC) with 95% CI will be tabulated.
- The distribution of antibody concentrations will be presented by histogram of anti-HAV log titer and also using reverse cumulative curves.

The seropositivity rate and the geometric mean concentrations (GMC) with 95% Confidence Intervals (CI) of antibody to hepatitis A virus (Anti-HAV) will be calculated and presented overall, by *Havrix* dose group, by follow up time class period after their last *Havrix* vaccination dose and by age class at the first *Havrix* dose.

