## **7. STATISTICAL CALCULATIONS**

### **7.1. Methods for calculating Confidence Intervals (CIs),**

All CI's will be 2-sided 95% CI.

- The exact 95% CIs for a proportion within a group will be calculated [[Clopper, 1934](#)].
- The standardized asymptotic 95% CI for the group difference in proportions will be calculated [[Robert, 1998](#)]: the standardized asymptotic method used within GSK Vaccine is **method 6**
- The 95% CI for Geometric mean concentrations (GMCs) will be obtained within each group separately. The 95% CI for the mean of log-transformed concentrations will be first obtained assuming that log-transformed values were normally distributed with unknown variance. The 95% CI for the GMCs will be then obtained by exponential-transformation of the 95% CI for the mean of log-transformed concentrations.
- The GMC ratio will be obtained using an ANOVA model on the logarithm based 10-transformed concentrations. The ANOVA model will include the dose group as fixed effect. The GMC ratio and its 95% CI will be derived as exponential-transformation of the log-transformed mean difference and its 95% CI.

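### The 1-dose versus 2-dose comparison is non-randomised and unadjusted for age at first dose, so it can be biased in either direction by an amount the documents do not allow to be estimated

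*SAP*

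**What the plan says.** **Allocation and eligibility.** The investigator places each child in a group according to the doses recorded in routine care (Protocol 6.5.7). The national schedule is described in Protocol 1.1: "Two doses of the vaccine were given to children at 12 and 18 months of age". The Amendment 2 rationale states: "The date of birth requirement has been eliminated from the study". Neither the inclusion criteria (Protocol 5.2) nor the according-to-protocol cohort definition (Protocol 8.3.3) limits age at first dose.

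**Use of age at first dose.** SAP 2 sets up sub-groups under "Age class at the first dose of Havrix", starting below 6 months and left open-ended beyond 18 months. SAP 6.1 summarises "age/age class [months] at the time of first and second dose of" vaccine per dose group and overall. SAP 6.2 reports seropositivity and GMC by dose group, by follow-up class "and by age class at the first" dose. SAP 7.2.2 gives the derivation.

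**The comparison.** The secondary objective is met if the lower 95% limit for 1 dose minus 2 doses is "greater than or equal to the pre-defined clinical non-inferiority limit of -10" percent (SAP 3.2). SAP 7.1 uses an unstratified interval for this ("The standardized asymptotic 95% CI for the group difference in proportions will be calculated") and an ANOVA on dose group alone for the GMC ratio. Protocol 8.6 specifies area of residence as a second fixed effect in that ANOVA. The SAP omits it and does not list the omission in its section 9 on changes.

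**Interpretation.** Protocol 8.7 calls the comparisons exploratory and rules out conclusions. SAP 6.2 says that meeting the limit demonstrates non-inferiority.

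**The concern.** Children who had one dose may differ from children who had two in the age at which they started. The variable is distinct from time since last dose: two 1-dose children who started at 12 and at 30 months can have the same interval to the visit. If antibody persistence, or the chance of natural exposure, also varies with starting age, part of the crude difference reflects the age mix and not the number of doses.

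The crude lower limit is what is read against -10%, and no planned analysis checks whether the reading survives adjustment. The SAP's two sensitivity analyses deal with exclusions from the according-to-protocol cohort (SAP 6.2) and suspected natural infection (SAP 9). At stake is a comparison meant to inform interest in a one-dose schedule (Protocol 1.1). A favourable bias could make 1 dose look non-inferior when it is not. An adverse bias could hide a true equivalence.

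**Working it through.** **Inputs from the documents:** 260 evaluable children per group, 80% seropositive in both groups, margin -10 points, stated power 80.9% (Protocol 8.2, Table 10). The test is "one-sided equivalence test of proportions (non-inferiority), alpha = 2.5%, power under equal proportions" (note to Table 10).

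**1. The plan's own figure.** SE = √(2 × 0.80 × 0.20 / 260) = 3.51 points. With the score variance constrained to the null (rates 74.1% and 84.1%), the null SE is 3.54 points. Power = Φ[(10 − 1.96 × 3.54) / 3.51] = Φ(0.87) = 80.9%, as stated. Exact enumeration of the score criterion gives 81.2%, and 2.5% when the true rates are 70% and 80%.

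**2. Size of a possible bias.** The crude shift is the sum over age classes of (1-dose share − 2-dose share) × seropositivity in the class. The documents give neither shares nor class rates, so both are **assumed**, for starts at <12, 12 to <18 and ≥18 months:

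- shares: 5/65/30% (1 dose) and 10/85/5% (2 doses)
- class rates 70/80/90%: 1 dose 3.5 + 52 + 27 = 82.5%; 2 doses 7 + 68 + 4.5 = 79.5%; shift **+3.0**
- class rates 75/80/85%: 3.75 + 52 + 25.5 = 81.25%; 7.5 + 68 + 4.25 = 79.75%; shift **+1.5**
- no age trend: shift **0**
- trend reversed: shifts of **-1.5** and **-3.0**

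**3. Effect on the criterion.**

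| Shift | True within-class difference | Crude rates, 1 vs 2 doses | Chance of meeting -10% |
|---|---|---|---|
| 0 | -10 | 70 vs 80 | 2.5% |
| +1.5 | -10 | 71.25 vs 79.75 | 5.9% |
| +3.0 | -10 | 72.5 vs 79.5 | 12.3% |
| 0 | 0 | 80 vs 80 | 81.2% |
| -1.5 | 0 | 78.75 vs 80.25 | about 67% |
| -3.0 | 0 | 77.5 vs 80.5 | about 50% |

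The first four rows are exact enumerations. The last two follow from Φ[(difference + 10)/SE − 1.96]: Φ(8.5/3.54 − 1.96) = Φ(0.44) and Φ(7.0/3.57 − 1.96) = Φ(0.00).

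**4. What stratification does.** With 260 per group the assumed mixes give 13/169/78 and 26/221/13 children. Mantel-Haenszel weights n₁n₂/(n₁+n₂) are 8.7, 95.8 and 11.1, or 7.5%, 82.9% and 9.6%. With class rates 70/80/90% and a true -10 in every class:

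- crude estimate: mean -7.0, SE 3.73 points by formula (3.75 in a 40,000-run simulation)
- stratified estimate: mean -10.0, SE 3.98 points (4.01 in simulation), criterion met 2.7% of the time

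With no true difference, the stratified SE is 3.69 points and power is Φ(10/3.69 − 1.96) = Φ(0.75), about 77%. Across the assumed trends it is 76 to 78%, against about 81% planned. If the age mixes are the same in both groups, stratification costs essentially no power.

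**The case against.** **The comparison is exploratory.** Protocol 8.7 allows no conclusions, and Protocol 8.8.2 and SAP 8.2 call all analyses descriptive. This limits the consequence, and it stands. It does not remove the point: the objective has a numerical pass rule and a power statement, and SAP 6.2 speaks of demonstration. A descriptive difference can also be confounded.

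**The tables will show any imbalance.** SAP 6.1 does tabulate age at first dose per dose group. SAP 6.2 does not make clear whether persistence is crossed by age class and dose group. That may be settled in the separate tables annex, which is not among the documents reviewed. Neither table is tied to the reading against -10%, and an adjustment chosen after seeing an imbalance would be post hoc.

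**Stronger readings that the documents do not support.** A reader might infer that the SAP regards age at first dose as a determinant of persistence. It uses it only as a reporting breakdown and never says so. A reader might also infer that late starters cluster in the 1-dose group, so the bias favours non-inferiority. Nothing shows this. The SAP derives age at second dose and the interval between doses, which allows for late second doses. Two-dose coverage of 11% in 2007 and 65% in 2008 (Protocol 1.1) fits programme roll-out as well as missed visits. The open-ended class list does not show that such children were enrolled.

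**Other confounders remain.** Residence, care-seeking and calendar period could matter as much. True. Age at first dose is simply already derived and already used for reporting, so adjusting for it is cheap.

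**Conclusion.** The point holds as a gap in the analysis. A non-randomised comparison is read against -10% without adjustment for a baseline variable that the SAP itself derives and reports by. The direction and size of any bias are unknown. The 0 to 3 point illustration, and the resulting 2.5% to about 12% or 81% to about 50%, rest wholly on the assumed age mixes and class rates. The bias is zero if either the mixes are equal or there is no age trend.

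It might be tempting to move the -10% criterion onto the stratified interval. The documents do not require that. The crude difference is the protocol's pre-specified comparison and the basis of Table 10, and under the assumed mixes the stratified interval would fall short of the planned 80% power. The supportable conclusion is that an age-stratified result should be pre-specified beside the crude one.

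**What to change.** 1. **SAP 6.2 and 7.1.** Keep the crude difference as the pre-specified result. Beside it, report a 1-dose minus 2-dose seropositivity difference stratified by age class at first dose, for example <12, 12 to <18 and ≥18 months. Use a Mantel-Haenszel or stratified Miettinen-Nurminen 95% CI, state a rule for merging sparse classes, and show it against -10%.
2. **Wording in SAP 6.2.** Describe non-inferiority as supported only if both results meet the limit, in exploratory terms that match Protocol 8.7, and not as demonstrated.
3. **GMC ratio in SAP 7.1.** Add age class at first dose to the ANOVA, together with the area of residence effect that Protocol 8.6 specifies.

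**Cost.** A few lines of SAP text and no new data: date of birth and vaccination dates are already collected (Protocol 6.5.5 and 6.5.7). The sample size need not change. The stratified interval is somewhat wider if the mixes differ as assumed (SE about 3.75 to 4.0 points, power about 76 to 78% on that interval). Requiring agreement guards against false non-inferiority, but does not recover power lost to an adverse bias; there, the stratified result will at least show the discrepancy. Some strata could be small, such as 13 late starters in the 2-dose group under the assumed mix. Confounding by other factors remains and should be stated in the report.

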6.5.5. Collect socio-demographic data

Record demographic data such as date of birth, gender, geographic ancestry, urban or rural residency in the subject's eCRF.

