6.5.7. Record medical history including hepatitis A disease or vaccination history

Obtain the subject's medical history by interview and/or review of the subject's medical records and record any pre-existing conditions or signs and/or symptoms present in a subject prior to participation in the study in the eCRF. Record any previous history of hepatitis A disease or vaccination. The investigator will also record if the subject received 1 dose or 2 doses of *Havrix* previously along with the vaccination dates, in order to assign the subject to the appropriate study group.

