- Ratio of the anti-HAV GMCs between the subjects who received only one dose of *Havrix* and subjects who received two doses of *Havrix* with their standardised asymptotic 95% CI at each serosurvey.

Computation of the GMC ratio and its 95% CI:

For all analyses (exploration evaluation of differences between groups), the GMC ratio and its 95% CI will be computed using an analysis of variance (ANOVA) model on the log10-transformed concentration with the group and area of residence as fixed effects in the model.

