8.7. Interpretation of analyses

All the analyses will be descriptive with the aim to characterise the immunogenicity within and between study groups. Because of the exploratory nature of the comparisons no conclusions can be made.

There will be no comparison between the two serosurveys (Year 8 and Year 10). It will be descriptive in nature.

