8.8. Conduct of analyses

Any deviation(s) or change(s) from the original statistical plan outlined in this protocol will be described and justified in the final study report.

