## 1. DOCUMENT HISTORY

Date	Description	Protocol Version
29-JAN-2018	Final version	Amendment 2 – 24 July 2017

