## 9. CHANGES FROM PLANNED ANALYSES

The histogram of anti-HAV log titer will be used to explore the possible outliers (subjects with very high concentrations that may have been elicited by natural HAV infection) in the study and if we detect a suspicious situation of natural infection we will do an additional analysis which determines a ‘natural infection cut-off’ by using the method described in the publication reference [[Wiedermann, 2007](#)] or a more appropriate method. We will perform a sensitivity analysis by excluding the potential outliers detected with the ‘natural infection cut-off’.

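### The SAP drops area of residence from the GMC-ratio model that the protocol specifies, and does not list the change

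*SAP*

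**What the plan says.** Protocol 8.6 gives one model for the ratio of GMCs between the dose groups, for all exploratory between-group comparisons: an ANOVA on "log10-transformed concentration with the group and area of residence as fixed effects in the model". SAP 7.1 keeps the log10 scale and the ANOVA but names a single term: "The ANOVA model will include the dose group as fixed effect". SAP 6.2, which introduces the ratio, names no covariate, and nothing elsewhere in the SAP puts residence back into the model.

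The SAP's document history cites "Amendment 2 – 24 July 2017" as its protocol version, which is the version supplied. The amendment entries in Protocol Appendix C do not touch the ANOVA sentence, so the two-term model is current protocol text. SAP section 9, on changes from planned analyses, covers only the search for natural infection among very high titres ("The histogram of anti-HAV log titer will be used to explore the possible outliers") and the sensitivity analysis that may follow from it.

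Four other places bear on the point:

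- Protocol 6.5.7: the number of earlier doses is recorded "in order to assign the subject to the appropriate study group".
- Protocol 6.5.5: residence is collected ("Record demographic data such as date of birth, gender, geographic ancestry, urban or rural residency"), and SAP 6.1 tabulates it by dose group.
- Protocol 8.7: "Because of the exploratory nature of the comparisons no conclusions can be made".
- Protocol 8.8: "Any deviation(s) or change(s) from the original statistical plan outlined in this protocol will be described and justified in the final study report".

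**The concern.** The two documents define two different estimates of the same quantity: one adjusted for residence, one crude. Nothing in the SAP says that the term was dropped on purpose, or why.

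The difference is not cosmetic, because the groups are formed by what happened to each child years earlier. Whether a child received the second dose may depend on where the family lived, and antibody levels may also differ by area, for example through natural exposure. If both hold, the crude ratio mixes the effect of the second dose with the effect of residence. Residence is the only covariate the protocol names for this comparison.

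Excluding children with known hepatitis A and the conditional outlier analysis in SAP section 9 deal with part of one pathway, natural infection. They do not replace the covariate.

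At stake is the interpretation of an exploratory ratio reported at Year 8 and again at Year 10. The primary endpoint, the within-group GMCs, the -10% seropositivity criterion and the sample size are not at stake.

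**Working it through.** **Comparing the texts**

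| Item | Protocol 8.6 | SAP 7.1 |
|---|---|---|
| Response | log10 concentration | log10 concentration |
| Fixed effects | group, area of residence | dose group |
| Listed in SAP section 9 as a change | – | no |

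Both sentences are complete, and the documents refer to the same amendment. Missing data do not explain the difference, since residence is collected and tabulated.

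**The plan's own figure.** The documents give no precision or power for the GMC ratio. Their only power figure, 80.9% in Protocol 8.2, is for seropositivity: 260 per group, 80% in both groups, margin 10 points, one-sided 2.5%. The unpooled normal approximation gives Φ(0.10/√(2×0.8×0.2/260) − 1.96) = Φ(0.89) = 81.3%, which reproduces it closely. The ANOVA terms do not enter this calculation.

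**Illustrative size of the difference between the models.** From the documents: 260 per group. Assumed, because the documents give no titres by residence and no residence split by dose group:

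- R: rural/urban GMC ratio
- d: rural share in the 1-dose group minus that in the 2-dose group
- residual SD of log10 concentration: 0.45 (range 0.30 to 0.60)
- an even rural/urban split overall

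*Bias.* Leaving out residence shifts the log10 difference by d × log10(R), so the crude ratio is multiplied by R^d.

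*Sampling error.* The CI half-width on the log10 scale is t(0.975, 518) × SD × √(2/260), with t = 1.9646:

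- SD 0.30: 0.0517, a factor of 1.13
- SD 0.45: 0.0775, a factor of 1.20
- SD 0.60: 0.1034, a factor of 1.27

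*Imbalance at which bias equals the half-width,* d = half-width / log10(R), for SD 0.30, 0.45 and 0.60:

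- R = 2: 0.17, 0.26, 0.34
- R = 1.5: 0.29, 0.44, 0.59

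*Coverage of the crude 95% CI for the residence-adjusted ratio, SD 0.45.* With rural shares s = 0.5 ± d/2, the crude SD is √(0.45² + s(1−s)(log10 R)²) and SE = crude SD × √(2/260). With k = bias/SE, coverage = Φ(1.96 − k) − Φ(−1.96 − k). For R = 2 and d = 0.2: crude SD = √(0.2025 + 0.24 × 0.0906) = 0.4735; SE = 0.0415; k = 0.0602/0.0415 = 1.45; coverage = 0.695.

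| R | d | Factor R^d | Coverage of crude CI |
|---|---|---|---|
| 1 | any | 1.00 | 95% |
| any | 0 | 1.00 | 95% |
| 1.25 | 0.1 | 1.02 | 94% |
| 1.5 | 0.1 | 1.04 | 93% |
| 2 | 0.1 | 1.07 | 89% |
| 1.5 | 0.2 | 1.08 | 86% |
| 2 | 0.2 | 1.15 | 70% |
| 2 | 0.3 | 1.23 | 41% |

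Simulation of the last three rows (4,000 runs each) gave 0.867, 0.696 and 0.410 for the crude interval, and 0.954, 0.955 and 0.948 for the adjusted one.

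**Cost of adjusting when it is not needed.** With R = 1 and an even split, the standard error grows by 1/√(1 − d²): 1.021 at d = 0.2 and 1.048 at d = 0.3.

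**The case against.** The strongest reply concerns weight. The ratio is an added exploratory comparison with no margin, criterion or power, and the protocol disclaims any conclusion from it. Protocol 8.6 leaves the detail of the analyses to the SAP, so the model that will be run can be identified. Protocol 8.8 asks for changes to be explained in the study report and does not require them in SAP section 9. The SAP also tabulates residence by dose group, so a reader would see any imbalance. This all stands, and it limits the importance of the point. It does not remove the conflict: dropping a term the protocol names is a change rather than a detail, and section 9 is the SAP's own place for changes. The ratio is also the only planned between-group comparison of GMCs, which are a stated secondary objective.

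A second reply is that the crude ratio is a legitimate descriptive estimate, being simply the ratio of the two tabulated GMCs, and that coverage figures presuppose an adjusted target. That is fair. The simulated 95% for the adjusted model holds only because residence is there the sole confounder and is measured without error. Residence recorded at the visit may differ from residence when the second dose was due, so adjustment may be incomplete.

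A third is that R, d and SD are all assumed. They are, and with d = 0.1 the effect is small. A minor technical point: at R = 2 the crude interval carries an SD of about 0.47, which moves the break-even d from 0.26 to about 0.27.

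**Conclusion.** The concern holds. The protocol and the SAP specify different models for the same ratio under the same amendment, and the SAP does not record the change. This follows from the text alone and needs no assumption.

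The numerical consequence cannot be computed from the documents. Under the assumptions above it runs from nothing (R = 1 or d = 0), through a factor of 1.02 to 1.07 at d = 0.1, to 1.23 at R = 2 and d = 0.3. Set against an assumed half-width factor of 1.20, it matters only if titres and second-dose uptake both differ clearly by residence. Its direction is unknown.

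The point should be corrected because the comparison is not randomised and the correction is cheap, but it does not threaten the main results. The seropositivity difference is unadjusted in both documents, and correcting this sentence leaves that as it is.

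**What to change.** Replace the model sentence in SAP 7.1 with, for example: *The ANOVA on log10 concentration will have dose group and area of residence (urban/rural, as recorded in the eCRF) as fixed effects; the GMC ratio and its 95% CI will be derived from the adjusted least-squares means.* Protocol 8.6 does not define area of residence. The urban/rural item is the likely variable, and the sponsor should confirm it. The crude ratio can be shown as supportive and listed in SAP section 9.

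If the sponsor prefers the dose-group-only model as the main one, that also resolves the conflict, provided section 9 lists it as a change from Protocol 8.6 and gives the reason.

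The cost is one sentence and one model term on data already collected. The interval widens by about 2% (d = 0.2) to 5% (d = 0.3) on the log scale if residence is unrelated to titre. Any child with missing residence drops out of the adjusted model, and the number should be reported.
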